#### **END OF OBSERVATION**

- 1. End of FU (i.e. end of study)
- 2. Drop-out (e.g., withdrawal of informed consent)
- 3. Loss to Follow-up

Supporting document SOP BMT 01.09 – Doc 5002.02 – Effective date 21.03.2017

## 3.3 Study variables

Table 1: Schedule of assessments and variables obtained during study phases.

	Ph	ase I	Phase II
	Baseline		FU 1
	Dd	seille	up to FU 8
	Physician	Patient	Patient
Informed consent		Before any procedure	
Patient characteristics			
- Age of women		х	
- Height			
- Weight		v	v
- BMI		Х	X
Socio-economic characteristics			
- Education		х	
- Smoking			
Endometriosis treatment	X		
- Diagnosis classification			

 
Prescribed medication
 
			

 
Number of surgical procedures (related to
 
	x		x
endometriosis)			

 
Reasons for switching / stopping treatment
 
			Х
Endometriosis characteristics			

 
Endometriosis pattern (symptoms, first
 
		х	
diagnosis, treatment history, pain)			

 
Surgical procedures related to endometriosis
 
		Х	Х
Gynecological History			

 
Age at first menarche
 
		х	

 
Pregnancies/deliveries
 
			
Medical history			
- Diseases / conditions		v	

 
Surgical procedures (other than
 
		X	
endometriosis-related)			
Family history		v	
(Endometriosis, Depression, VTE)		Х	
Medication		Х	Х
Anemia		Х	Х
Depression		Х	Х
Mood		Х	Х
Serious Adverse events			Х

### 4. Power and Sample Size

The 2 to 7-year follow-up of more than 25,000 women should result in approximately 89,000 documented women-years. This estimate is based on the assumptions that (1) ZEG's physicians' network could recruit 25,000 women within three years, and (2) the annual drop-out rate is 10% (based on the EURAS-OC [4] and LASS studies). Details are provided in Table 1 and are based on the assumption that the follow-up period is a maximum of 6 years.

**Table 1:** Expected observation time (max. 6 years follow-up): Patient recruitment within 3 years (annual recruitment rate = 8,334 women)

	Sub-cohorts recruited during the					
	1 st study year		2 nd study year		3 rd study year	
Time (y)*	No. of women	Time of observation	No. of women	Time of observation	No. of women	Time of observation
1	7,910	4,035				
2	7,119	7,515	7,910	4,035		
3	6,407	6,763	7,119	7,515	7,910	4,035
4	5,766	6,087	6,407	6,763	7,119	7,515
5	5,190	5,478	5,766	6,087	6,407	6,763
6	4,671	4,930	5,190	5,478	5,766	6,087
WY (total)		34,808		29,878		24,400
WY (grand total)	89,086					

\* Time after start of recruitment

The study was designed to analyze rare events (according to the CIOMS classification 1-10 and less than 1 event(s) per 10,000 women-years, respectively). The adverse events of particular interest for the sample size calculations are anemia, clinically relevant depression and treatment failure.

The background prevalence of anemia in premenopausal European women is approximately 10-15% [5]. Based on this high prevalence and the fluctuating character of the disease the investigators anticipate an incidence of new or recurrent anemia in an active surveillance study of 0.01-0.02. The sample size calculation is based on a conservative estimate of 0.01 (or 1 event per 100 WY).

A conservative estimate of the prevalence rate for depression in women with endometriosis is 20%. This figure is based on a systematic literature review of the available evidence and an analysis of EURAS/INAS results. For newly diagnosed or worsening depression the expected incidence rate is at least 0.01. Based on this incidence, the sample size outlined below was calculated; in case the study

11

\*\* The number of recruited women equals 8,334. However, the number of women at the end of the first year is lower because some women will drop out during the first year (daily drop-out rate is ~ 0.029%).

 ${\bf 9}$  According Study Protocol, Amendment of September 30, 2017

Supporting document SOP BMT 01.09 – Doc 5002.02 – Effective date 21.03.2017

shows other incidence rates at a later point in time, a re-calculation may be necessary and will be discussed with the Safety Monitoring and Advisory Council if required.

Based on the natural history of endometriosis treatment, we anticipate that the majority of women will stop or change treatment regimen during the course of this study. We expect an incidence rate of women ceasing or changing treatment ('treatment failure') for other endometriosis medications due to lack of efficacy, loss of efficacy or an adverse drug reaction of at least 0.3. For the DNG cohort, a proportion of 0.25 of the total study population seems to be realistic.

Overall, 3 hypotheses will be tested (cf. section 11). The problem of multiple comparisons is addressed by using Bonferroni-Holm correction to maintain the overall error rate by testing each individual hypothesis at a statistical significance level of 1/3 times what it would be if only one hypothesis were tested (i.e., the individual tests will be based on an  $\alpha$  level of 0.0167 instead of 0.05).

Power calculations based on the incidences given above showed that approximately 84,000 womenyears would be needed to show non-inferiority of DNG versus other endometriosis medications for anemia. The calculations for anemia are based on the assumptions given in Table 2. In essence, the study is powered to exclude a two-fold risk of anemia for the DNG with at least 10% of the total exposure – if the true risk of anemia is not different for the relevant sub-cohorts.

**Table 2:** Power calculation [6] for anemia based on the assumption that the true incidence of DNG cohort is not different from other endometriosis medications (reference cohort)

Test significance level, α (one-sided)	0.0083 (= 0.0167 two-sided)
Anemia Incidence for reference cohort	0.01
Non-inferiority margin	0.01 (equal to the anemia incidence for the reference cohort)
Expected anemia incidence for DNG cohort	0.01
Power (%)	90
Proportion of DNG users (% of study population)	10
Proportion of reference users (% of study population)	5
Required women-years in DNG cohort	8,400
Required women-years in reference cohort	4,200
Total women years	84,000

Furthermore, 84,000 WY would be sufficient to also exclude a two-fold risk of clinically relevant depression (cf. Table 3), assuming that DNG accounts for at least 10% of the total exposure.

Supporting document SOP BMT 01.09 – Doc 5002.02 – Effective date 21.03.2017

For 'treatment failure' approximately 29,500WY will be required to show that DNG is superior to other endometriosis medications (cf. Table 4), assuming that the proportion of DNG, danazol, and GnRH agonists users each account for 10% of the total exposure.

**Table 3:** Power calculation [6] for depression based on the assumption that the true incidence in the DNG cohort is not different from the reference cohort

Test significance level, $\alpha$ (one-sided)	0.0083 (= 0.0167 two-sided)
Depression Incidence for reference cohort	0.01
Non-inferiority margin	0.01 (equal to the depression incidence for the reference cohort)
Expected depression incidence for DNG cohort	0.01
Power (%)	90
Proportion of DNG users (% of study population)	10
Proportion of reference users (% of study population)	5
Required women-years in DNG cohort	8,400
Required women-years in reference cohort	4,200
Total women years	84,000

Supporting document SOP BMT 01.09 - Doc 5002.02 - Effective date 21.03.2017

**Table 4:** Power calculation [6] for 'treatment failure' based on the assumption that the true incidence in the DNG cohort is ~ 2,500/10,000 compared to ~ 3,000/10,000 in the other endometriosis medications cohort.

Test significance level, α (one-sided)	0.0167
Incidence of treatment failure for other endometriosis medications cohort	0.30
Clinically relevant difference	0.05
Expected incidence of treatment failure for DNG cohort	0.25
Power (%)	90
Proportion of DNG users (% of study population)	10
Proportion of reference users (% of study population)	5
Required women-years in DNG cohort	2,950
Required women-years in other endometriosis medications cohort	1,475
Total women years	29,500

These power calculations suggest that this study is sufficiently powered to show non-inferiority of DNG compared to established endometriosis treatments with regard to anemia and clinically relevant depression, as well as superiority with regards to 'treatment failure'.

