1. INTRODUCTION

Endometriosis is a common, chronic, gynecological disease characterized by pain and impaired fertility. Prevalence estimates vary widely, however, the proportion of premenopausal women living with endometriosis is thought to be approximately 10% [1]. Endometriosis causes chronic inflammation, ovarian cyst formation, fibrosis and adhesions [1]. There seems to be little correlation between the extent of the disease and severity of pain experienced [2]. However, symptoms seem to respond to decreased circulating estrogen [3] and the mainstay of medical treatment is hormonal induced anovulation and a reduction in endogenous estrogen production.

While currently approved medications for endometriosis have proven to be effective in decreasing pelvic pain, many have clinically relevant side-effects. Danazol, a testosterone analogue, can cause androgenization and GnRH agonists are known to decrease bone mineral density. Consequently, treatment for endometriosis with these medications needs to be stopped after 6-12 months. Post-treatment endometrial lesions tend to regenerate, with many women's symptoms reoccurring 1-2 months after the cessation of treatment. Some countries in Europe also allow the use of progestogens for the treatment of endometriosis, however, there is currently no pharmaceutical preparation licensed for the treatment of endometriosis in all member states of the European Union.³

Dienogest (DNG) is a 19-nortestosterone derivative progestogen that is highly selective for progesterone receptors [4]. DNG has been available as part of a low-dose combined oral contraceptive containing 2mg of dienogest and 30µg of ethinylestradiol (DNG/EE) in Germany since 1995. As a progestin in DNG/EE, DNG is known for having strong endometrial effects that improve dysmenorrhoea and decrease the duration of menstrual bleeding [5]. In addition, progestogens may also modulate pain associated with endometriosis by dampening neuronal activity [3]. As a monotherapy for the treatment of endometriosis DNG 2mg/day has been available in Japan since 2008. In Japan it has been found to be a reliable and effective treatment for dysmenorrhea, premenstrual pain, dyspareunia and diffuse pelvic pain associated with endometriosis associated pelvic pain with improved tolerability compared with 3.75mg leuprolide acetate (LA) [7-8]. Unlike LA, DNG has minimal effects on bone density and may offer women a new option for the long-term control of endometriosis symptoms.

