#### 3.1 Study population, inclusion and exclusion criteria

It was planned to implement the study in several European countries including, but not necessarily limited to, Germany, Austria, France, and Poland. However, the study was initiated in Germany in 2010, and in Hungary and Poland in early 2011. Because of recruitment problems, additional countries were included to broaden the recruitment base: Ukraine, Russia, and Switzerland started recruitment in 2012.

Recruitment of the cohort members will be conducted via a network of approximately 1,000 physicians (study centers) managing women with a diagnosis of endometriosis. The combined cohort will include 25,000 women .

At the participating centers, all women prescribed a new treatment for endometriosis are to be asked by their physician if they are willing to participate. The physician is to explain the nature of the study, its purpose and associated procedures, and the expected duration of follow-up for each woman prior to her study entry. Each woman is to have ample opportunity to ask questions and must be informed about her right to withdraw from the study at any time without disadvantage and without having to provide reasons for her decision. This information will be provided on an informed consent and data privacy form which must be signed by all study participants. These documents are to be approved by the relevant local Ethics Committees and the relevant Data Privacy Office, if applicable.

Once enrolled, a subject may discontinue use of the relevant medication at any time. However, subjects will continue to be followed whether or not they remain on their treatment for endometriosis, provided that they do not withdraw their consent. During the follow-up phase, subjects will be asked whether they have discontinued their treatment or whether they have switched to another medication or received surgical treatment to manage their endometriosis. Information on the date and reason for discontinuation or switching during the follow-up phase will also be collected.

The study participants are women who

- are users of a newly prescribed regimen for endometriosis (starter, switcher or restarter)
- are willing to participate in this long-term follow-up study.

There are no specific medical inclusion or exclusion criteria. However, women

- who are not cooperative/available for follow-up may be excluded from study participation

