- women with a language barrier will not be eligible for study inclusion.

The study flowchart (section 3.2) provides an overview of all study phases.

 At the end of recruitment in June 2014 the number of OED patients was much lower than the anticipated share of 10% of the study population. The SMAC recommend therefore to re-start recruitment for 2,000 OAED patients.

Supporting document SOP BMT 01.09 - Doc 5002.02 - Effective date 21.03.2017

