#### 5.1 Analysis sets

There are no specific inclusion or exclusion criteria. However, women with a language barrier, a non-hormonal or not newly prescribed baseline medication or women who are pregnant at study enrollment will be excluded from the analysis. The final analyses will include both an "as treated" (AT) and an "intention-to-treat" (ITT) analysis. All women who are not excluded from the analysis will be assigned to the ITT and AT population at baseline. Only women with follow up information will be considered for longitudinal analysis (e.g. distribution of outcomes over time, incidence rates, regression). Women who never started their prescribed baseline medication will be considered in the ITT analysis, but excluded from the AT analysis. The safety conclusions of the study will be based on the AT analysis.

Supporting document SOP BMT 01.09 – Doc 5002.02 – Effective date 21.03.2017

This study follows three cohorts: users of Visanne (DNG), users of other medication approved for the treatment of endometriosis (OAED) and users of non-approved hormonal medications prescribed for endometriosis treatment or those approved only in some participating countries (NAED).

Distribution of women, population characteristics (baseline and follow up) as well as clinical outcomes will be presented for the following cohorts and sub-categories.

Cohort Sub-category for presentation	
DNG	Complete cohort
OAED	GnRH-a, Danazol, complete cohort
NAED	Combined hormonal contraceptives, other progestins, complete

The cohorts consist of new users (starter and restarter) or switcher of a hormonal endometriosis treatment. For the primary analysis, outcomes of interest or adverse events will be assigned to the treatment at the time the outcome or the event occurred. Women with multiple exposure or unspecific treatment will be specified as "Allocation unknown". Women who stopped their treatment will be assigned to an "Ex-use" cohort.

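### Tables 2 and 3 count 5% of users as 5% of all observation time, so reaching 84,000 total women-years does not secure 90% power in the deciding as-treated comparison with GnRH agonists and danazol

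*SAP*

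**What the plan says.** SAP section 4 (and Protocol section 12, with the same tables) sizes both non-inferiority tests identically: one-sided alpha 0.0083, incidence 0.01 in both cohorts, a margin equal to a doubling, and 90% power. DNG users are set at 10% and reference users at 5% of the study population. The required exposure is 8,400 DNG WY, 4,200 reference WY and 84,000 WY in total. The text concludes that "the study is powered to exclude a two-fold risk of anemia for the DNG with at least 10% of the total exposure". For anemia, "the investigators anticipate an incidence of new or recurrent anemia in an active surveillance study of 0.01-0.02"; the lower figure is used.

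Four other statements bear on this:

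- **Comparator.** SAP section 5.2 tests DNG against OAED, which sections 3.2 and 5.1 define as GnRH agonists and danazol.
- **Duration of use.** Of danazol and GnRH agonists, Protocol section 1 says that "treatment for endometriosis with these medications needs to be stopped after 6-12 months".
- **What is followed.** Under SAP section 3.1, "subjects will continue to be followed whether or not they remain on their treatment for endometriosis". Total WY therefore includes time off drug.
- **What is counted.** Under SAP section 5.1, "outcomes of interest or adverse events will be assigned to the treatment at the time the outcome or the event occurred", and "Women who stopped their treatment will be assigned to an" ex-use cohort. The same section states: "The safety conclusions of the study will be based on the AT analysis".

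SAP section 3 extends follow-up by a year in order to reach 84,000 total WY. Footnote 8 in section 3.1 reports that "the number of OED patients was much lower than the anticipated share of 10% of the study population" and that the advisory council recommended restarting recruitment for 2,000 OAED patients. Section 4 keeps the power figures and the conclusion of adequate power unchanged.

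**The concern.** The tables turn a share of women into an equal share of women-years. That is valid for an analysis that counts all follow-up by baseline prescription. It is not valid for the as-treated analysis when the reference drugs are used for a small part of follow-up. Neither document shows a step from number of users to current-use WY.

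The smaller cohort limits precision, so both non-inferiority tests depend mainly on OAED events during treatment. If those are few, the interval is wide and a hazard ratio of 2 may not be excluded even when the true ratio is 1. A reader told that power was 90% would take that as a signal about DNG when it could be low power. The total used to justify the longer follow-up does not measure the exposure that matters.

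**Working it through.** **Inputs.** From SAP section 4: one-sided alpha 0.0083, true hazard ratio 1, margin 2, incidence i = 0.01 (range 0.01-0.02), 25,000 women, 10% yearly drop-out, yearly treatment failure of 0.3 on the reference drugs. From Protocol section 1: 6-12 months of use. **Assumption:** one course per reference woman and no other OAED time, unless stated.

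**Formula.** With events E = WY × i in each cohort,

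power = Φ( ln 2 / √(1/E_DNG + 1/E_OAED) − 2.395 ).

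**Plan's own figure.** E_DNG = 84 and E_OAED = 42 give √(84×42/126) × 0.693 = √28 × 0.693 = 3.668, so power = Φ(3.668 − 2.395) = 0.898. The tables reproduce. The formula is sound and the fault lies in the exposure put into it.

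**The conversion.** 5% × 84,000 = 4,200 WY; 5% × 25,000 = 1,250 women; 4,200/1,250 = 3.36 years on drug per woman. The plan's mean follow-up is 89,086/25,002 = 3.56 years. Five percent of women on drug for 0.5-1 year therefore supply 5% × 0.5/3.56 = 0.7% to 5% × 1/3.56 = 1.4% of all WY, not 5%.

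**OAED current-use WY needed for 90% power.** The information required is ((2.395 + 1.282)/0.693)² = 28.14, so OAED WY = 1/(i/28.14 − 1/WY_DNG). The 20,000 and 44,500 DNG figures are illustrative.

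| DNG WY | i = 0.01 | i = 0.02 |
|---|---|---|
| 8,400 | 4,232 | 1,690 |
| 20,000 | 3,275 | 1,514 |
| 44,500 | 3,004 | 1,453 |
| unlimited | 2,814 | 1,407 |

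**Power with one 6-12 month course, DNG at 8,400 WY.**

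| OAED women | OAED WY | i = 0.01 | i = 0.02 |
|---|---|---|---|
| 1,250 (5%) | 625-1,250 | 24-46% | 49-80% |
| 3,250 (1,250 + 2,000) | 1,625-3,250 | 56-83% | 89-99% |
| 4,500 (2,500 + 2,000) | 2,250-4,500 | 70-91% | over 95% |

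The last row is an upper bound, because footnote 8 says the 10% share was far from reached.

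- With 1,250 women and unlimited DNG time, power is 25-52% at 0.01 and 52-86% at 0.02. The 1,250 WY lie below the 1,407 floor, so 90% is not reached within the anemia range under this assumption.
- With 3,250 women, 12-month courses and i = 0.01, power is about 90% with 20,000 DNG WY and 92% with 44,500.
- For depression the plan says at least 0.01 and gives no upper figure. With 1,250 OAED and 8,400 DNG WY, 90% needs i ≥ 28.14 × (1/8,400 + 1/1,250) = 0.026.

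**Allowing for attrition.** Failure of 0.3 plus drop-out of −ln 0.9 = 0.105 gives a yearly rate of 0.405. Mean time on drug is (1 − e^(−0.405T))/0.405, which is 0.453 years for T = 0.5 and 0.822 for T = 1. Power at 0.01 becomes 21-38%, 52-77% and 66-87% for 1,250, 3,250 and 4,500 women. At 0.02 it is 45-72%, 86-98% and 94-99%.

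**The added year.** Recruitment ended in June 2016 (SAP section 3.2), so a 12-month first course ends by about June 2017. The extension runs to the end of the second quarter of 2018, and the added year brings almost no first-course OAED time.

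**The case against.** The strongest reply is that the tables contain no arithmetic error and already list required WY by cohort; what is missing is an exposure assumption. That is true, but the table labels the 5% as users and the WY total depends on that equality.

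Other points have some force:

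- **ITT.** An intention-to-treat analysis of anemia and depression is also planned, and 5% of users is then about 5% of WY. It does not decide the safety conclusions.
- **Carry-over.** The mock SAE tables attribute events within three months of stopping to the last treatment. Extending that to these outcomes would give 938-1,563 OAED WY from 1,250 women and power of 35-55% at 0.01. At 0.02, with 12-month courses and 20,000 DNG WY, it would reach 91%. The rule is written only for the SAE tables, and section 5.1 moves stopped women to ex-use.
- **Extra recruitment.** The restart for 2,000 women addresses the limiting cohort, and favourable combinations then reach 90%. The SAP does not give the number achieved or recompute power.
- **Recalculation.** Protocol section 12 provides for one after two years, and SAP section 4 if incidence differs. They name incidence and drop-out, not on-treatment exposure by cohort.
- **Comparator.** The protocol's comparator, approved hormonal medications, is wider than the SAP's. The point therefore applies most directly to the SAP.
- **Reference share.** Sizing on 5% while expecting 10% can be deliberate caution, and the 10% each for danazol and GnRH agonists belongs to the treatment-failure calculation. The documents do not explain the difference.

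**Conclusion.** The concern holds. The 90% power in Tables 2 and 3 requires about 4,200 current-use OAED WY alongside 8,400 DNG WY at an incidence of 0.01, and reaching 84,000 total WY does not ensure that. The shortfall is large in the plan's own 5% case and moderate to nil once the 2,000 extra women, higher incidence or much larger DNG exposure are assumed.

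The size is conditional. The documents report no OAED current-use WY, and later switches into OAED, repeat courses and add-back regimens would add time that cannot be quantified from them. The consequence is an overstated power claim and a risk of misreading an inconclusive result; it does not bias the tests toward non-inferiority.

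**What to change.** In SAP section 4:

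1. State the requirement as current-use WY, or confirmed events, separately for OAED and DNG, with the OAED need given jointly with DNG exposure and incidence as in the first table above.
2. Replace the 90% figure and the conclusion of adequate power with the power at the OAED and DNG current-use WY accrued or projected, over incidences of 0.01-0.02.
3. Use one reference share throughout, or explain why 5% (Tables 2-4), 10% (footnote 8) and 10% for each drug (treatment-failure text) differ.
4. Judge the adequacy of follow-up in section 3 on OAED current-use WY or events, not on 84,000 total WY.

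The cost is SAP wording and a recalculation from data already held; the stated power may become less favourable. No added recruitment and no change to treatment duration is proposed.

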A conservative estimate of the prevalence rate for depression in women with endometriosis is 20%. This figure is based on a systematic literature review of the available evidence and an analysis of EURAS/INAS results [10-12]. For newly diagnosed or worsening depression the expected incidence rate is at least 0.01. Based on this incidence, the sample size outlined below was calculated; in case the study shows other incidence rates at a later point in time, a re-calculation may be necessary and will be discussed with the Safety Monitoring and Advisory Council if required.

Based on the natural history of endometriosis treatment, we anticipate that the majority of women will stop or change treatment regimes during the course of this study. We expect an incidence rate of women ceasing or changing treatment ('treatment failure') for other endometriosis medications due to lack of efficacy, loss of efficacy or an adverse drug reaction of at least 0.3. For the DNG cohort a proportion of 0.25 of the total study population seems to be realistic.

Overall, 3 hypotheses will be tested (cf. section 11). The problem of multiple comparisons is addressed by using Bonferroni-Holm correction to maintain the overall error rate by testing each individual hypothesis at a statistical significance level of 1/3 times what it would be if only one hypothesis were tested (i.e., the individual tests will be based on an α level of 0.0167 instead of 0.05).

Power calculations based on the incidences given above showed that approximately 84,000 women-years would be needed to show non-inferiority of DNG versus other endometriosis medications for anemia. The calculations for anemia are based on the assumptions given in Table 2. In essence, the study is powered to exclude a two-fold risk of anemia for the DNG with at least 10% of the total exposure – if the true risk of anemia is not different for the relevant sub-cohorts.

Table 2: Power calculation^[15] for anemia based on the assumption that the true incidence of DNG cohort is not different from other endometriosis medications (reference cohort)

Test significance level, α (one-sided)	0.0083 (= 0.0167 two-sided)
Anemia Incidence for reference cohort	0.01
Non-inferiority margin	0.01 (equal to the anemia incidence for the reference cohort)
Expected anemia incidence for DNG cohort	0.01
Power (%)	90
Proportion of DNG users (% of study population)	10
Proportion of reference users (% of study population)	5

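### Table 4 sizes the treatment-failure superiority test at 0.0167 one-sided, while Tables 2 and 3 apply the same one-third multiplicity rule as 0.0083 one-sided, and the difference is not explained

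*SAP*

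**What the plan says.** Protocol section 12 and SAP section 4 carry the same rule and the same tables.

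- **Rule.** The SAP says "Overall, 3 hypotheses will be tested". Protocol section 12 invokes a Bonferroni-Holm correction, described as "testing each individual hypothesis at a statistical significance level of 1/3 times what it would be if only one hypothesis were tested", so that "the individual tests will be based on an α level of 0.0167 instead of 0.05". That sentence does not say whether 0.05 and 0.0167 are one-sided or two-sided.
- **Tables 2 and 3** (anemia and depression, non-inferiority). The row for the one-sided level reads "0.0083 (= 0.0167 two-sided".
- **Table 4** (treatment failure, superiority). The text introducing it says "For 'treatment failure' approximately 29,500WY will be required to show that DNG is superior to other endometriosis medications". The same row reads "Test significance level, α (one-sided) 0.0167", with no two-sided equivalent. The planning assumption is "true incidence in the DNG cohort is ~ 2,500/10,000 compared to ~ 3,000/10,000 in the other endometriosis medications cohort", with "Clinically relevant difference 0.05", 90% power, and DNG and reference at 10% and 5% of exposure. The result is 2,950 and 1,475 women-years, 29,500 in total.

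Neither document says why treatment failure has a different level.

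**The concern.** Treatment failure is one of three primary outcomes and the only superiority claim. Under one rule, two tests are planned at 0.0083 one-sided and the third at twice that.

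This matters because SAP section 5.2 states the treatment-failure hypotheses one-sided, as an odds ratio of at least 1 against below 1. The Cox model section (5.4.2.1) names only 95% limits. Table 4 is therefore the only place that gives a one-sided level for this test. Someone who takes the level from it could declare superiority at twice the level applied to the two safety outcomes. The power and women-years in Table 4 also depend on that entry.

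**Working it through.** **Inputs.** All come from protocol section 12 and SAP section 4: 0.25 (DNG) against 0.30 (reference), 2:1 allocation, 90% power (z = 1.282), 2,950/1,475 women-years. One-sided 0.0167 has z = 2.127. One-sided 0.05/6 = 0.00833, printed as 0.0083, has z = 2.394.

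**1. Levels.** 0.0083 + 0.0083 + 0.0167 = 0.0333 one-sided. Half of a two-sided 0.05 is 0.025. One-sided 0.0167 is 0.0333 two-sided, which is not a Holm step for three tests (two-sided 0.0167, 0.025, 0.05).

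**2. Table 4 at its own level, proportion scale.** Women-years are treated as numbers of women.

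- Unpooled standard error: √(0.21/1,475 + 0.1875/2,950) = 0.01435.
- Pooled, with p = 0.8/3: √(0.1956 × (1/1,475 + 1/2,950)) = 0.01410.
- Unpooled power: Φ(0.05/0.01435 − 2.127) = Φ(1.357) = 91.3%.
- Pooled power: Φ((0.05 − 2.127 × 0.01410)/0.01435) = Φ(1.394) = 91.8%.

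So on this scale Table 4 reaches its 90% at its own level. The requirement there would be 1,382 (pooled) to 1,412 (unpooled) reference women-years, 4–6% below the stated 1,475. The pooled formula returns exactly 1,475 at one-sided 0.0125 (two-sided 0.025), but the documents do not say that this level was used.

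**3. The same women-years at 0.0083 one-sided.**

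- Unpooled: Φ(3.484 − 2.394) = Φ(1.090) = 86.2%.
- Pooled: Φ((0.05 − 2.394 × 0.01410)/0.01435) = Φ(1.132) = 87.1%.

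**4. Requirement for 90% power at 0.0083 one-sided, proportion scale.**

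- Unpooled reference: (2.394 + 1.282)² × (0.21 + 0.1875/2)/0.05² = 1,641; DNG 3,283.
- Pooled reference: (2.394 × √(0.1956 × 1.5) + 1.282 × √0.30375)²/0.05² = 1,605; DNG 3,209.

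The rounded level 0.0083 gives 1,643/3,286 and 1,606/3,212. Dividing DNG women-years by 0.10 gives totals of about 32,100–32,900.

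**5. If 0.25 and 0.30 are rates per woman-year.** With an events formula, d = (z_α + 1.282)²/((2/9) × θ²), θ = ln(0.30/0.25) = 0.1823. The stated women-years yield 737.5 + 442.5 = 1,180 events.

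- Power: √(1,180 × 2/9) × 0.1823 = 2.952. Subtracting 2.127 gives 79.5%; subtracting 2.394 gives 71.2%.
- Requirement at 0.0083: d = 1,829 events. Dividing by the mean rate 0.8/3 gives 6,858 women-years, or 4,572/2,286, and a total of about 45,700.

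With θ = ln 2 and a rate of 0.01, this formula gives 8,435/4,218 for Table 2, close to the stated 8,400/4,200. For Table 4 at 0.0167 it gives about 3,930/1,970, not 2,950/1,475.

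**6. Effect on the study total.** At 8,400/4,200 women-years and 0.0083 one-sided:

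- Proportion scale: power above 99.9%.
- Rate scale: 2,100 + 1,260 = 3,360 events; √(3,360 × 2/9) × 0.1823 = 4.98; Φ(4.98 − 2.394) = 99.5%.

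**The case against.** **Sidedness.** The rule does not say that 0.05 is two-sided. If it is one-sided overall, Table 4 complies, and the sum of 0.033 lies below 0.05. This stands as far as it goes. But Tables 2 and 3 would then use half their share while calling 0.0167 two-sided, so the tables conflict on either reading.

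**Holm.** The procedure named is step-down, so a hypothesis reached later may be tested at 0.0125 or 0.025 one-sided. This is right for the final analysis. It does not explain 0.0167 one-sided in a planning table, and the text fixes every test at one third.

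**Table 4 is only a planning table.** No passage says that treatment failure will be tested at its level. A reader might infer that the analysis will exceed the stated error rate; the documents do not establish that. They show an inconsistent planned level.

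**Power.** A reader might infer that 2,950/1,475 falls short of 90% outright. On the proportion scale it does not at Table 4's own level; the shortfall appears once the level is 0.0083.

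**Scale.** A reader might take 71% and 45,700 women-years as the main result. The documents are mixed. An incidence rate for the reference, units of women-years, and a planned rate ratio and Cox model (SAP section 8, D-3) point to rates. A proportion for DNG, a 5-percentage-point difference, an odds-ratio hypothesis (SAP 5.2) and an incidence proportion (SAP section 8, C-1) point to proportions. Nor can Table 4 be said to misapply its cited method, since neither document prints the formula. The rate figures are therefore an alternative only.

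**Study size.** SAP footnote 8 reports a reference share well below plan, which might suggest that treatment failure is underpowered. Every corrected reference requirement (about 1,610 to 2,290) is below the 4,200 already needed for anemia and depression, so this error adds no new constraint.

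**Conclusion.** The inconsistency is on the page: one rule, two one-sided levels, and no justification. If 0.05 is two-sided overall, as Tables 2 and 3 imply, Table 4's level is twice its share, and the planned one-sided levels sum to 0.033 instead of 0.025. If 0.05 is one-sided, Tables 2 and 3 are the ones out of line.

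On the first reading and the proportion scale, the stated 90% power becomes about 86–87%, a loss of 3–4 points, and the requirement rises from 29,500 to about 32,100–32,900 women-years. If rates were meant, power is about 71% and the requirement about 45,700. Relabelling 0.0167 as two-sided would not be enough, because the women-years would then need recalculation.

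The consequence is for error control and for the stated requirement of a primary hypothesis. The study's planned size is unaffected, provided that exposure reaches 8,400 and 4,200 women-years.

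**What to change.** - Set Table 4 to 0.0083 one-sided (= 0.0167 two-sided) in both documents, and say in the multiplicity sentence that 0.05 is two-sided.
- Name the scale of 0.25 and 0.30. For proportions, restate the requirement as about 3,210–3,290 DNG and 1,610–1,640 reference women-years (total about 32,100–32,900), or keep 2,950/1,475 and restate power as about 86–87%. For rates, the matching figures are about 4,570/2,290 (total about 45,700), or about 71% power.
- Judge treatment failure under the same Bonferroni-Holm rule and the same sidedness as the other two tests, or state and justify an unequal split.

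The cost is a few table entries and a sentence or two. The stated requirement becomes less favourable, but no additional women are needed and the 84,000 women-year target stays as it is.
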